Diagnosis and Main Inclusion Criteria	
 • Biopsy-proven local recurrence of prostate adenocarcinoma (biopsy within 182 days) • Pathologic Fluciclovine uptake in pelvic lymph nodes without distant metastases • Current AUA International Prostate Symptom Score (IPSS) score <20 • Initial disease stage cT1-3a NX or N0 • Treated with prior definitive radiation therapy using any radiotherapeutic modality (prior whole pelvis RT ineligible)
Duration of Administration	2 brachytherapy implants, ~5-8 weeks of daily radiation, 6 months hormonal therapy
Statistical Methodology	
This study is designed as a two stage Phase I/II, non-randomized study. In the first stage, 7 patients will be accrued. If there are 2 or more toxic responses in these 7 patients, the study will be stopped for safety reasons. Otherwise, 17 additional patients will be accrued for a total of 24 patients.
 
Assuming that the true toxicity rate in the population is 10% or less, the study is powered to reject the null hypothesis that the toxicity rate is 33% or higher. A toxicity event is defined as an acute grade ≥ 3 radiation-related toxicity as assessed by the Common Toxicity Criteria for Adverse Events version 4.
 
Standard non-parametric or parametric methods will be used to describe these patients' demographic and clinical information as well as their dosimetric information. The primary aim of the study is to estimate the toxicity rate of HDR brachytherapy among patients with recurrent prostate cancer. A one-tailed test for a difference in proportions will be used to determine whether the observed toxicity rate is lower than the hypothesized toxicity rate. The null hypothesis that the toxicity rate is 33% or higher will be rejected if more than 19 (non-toxic) responses are observed in 24 patients. When the true toxicity rate is 10.0%, this design yields a type I error rate of .046 and power of 81%.
 
We also will describe the freedom from biochemical recurrence, relapse-free survival, local control, elsewhere-prostate control, freedom-from local failure, freedom from distant metastasis, freedom from hormonal therapy, disease-free survival, cause-specific survival, and overall survival.

Study Schema

LU 210546

Version 10/23/17

Table of Contents

Title page.....	i
Signature page.....	iv
Study Summary.....	v-vi
Study Schema	vii
List of Abbreviations	x
1.0 Background and Rationale	1
1.1 Disease Background and Lessons from Other Malignancies	1

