There is evidence supporting salvage HDR for patients with locally recurrent prostate cancer, primarily delivered to the whole prostate gland due to uncertainty about the geographic location of the local recurrence with older imaging techniques. Yamada, et al reported their results of a phase II study of 42 patients treating LRPC with salvage HDR brachytherapy after prior definitive external radiation. Their prescribed dose was 32Gy delivered in four fractions over 30 hours using a single implant. At a median follow-up up 26 months, they reported an actuarial 5-year biochemical recurrence free survival of 68.9% and a distant metastasis free survival of 81.5%. Regarding toxicities, acute genitourinary (GU) grade 1 and 2 toxicities rates were 38% and 40%, respectively, and 38% and 48% had late grade 1 or 2 GU toxicities. Only 1 of 42 patients developed late grade 3 toxicity of urinary incontinence, and 3 patients (7%) developed a late grade 3 urinary stricture corrected with urethral dilatation. Late grade 1-2 gastrointestinal (GI) toxicities occurred in 43% and 14% of patients, but there were no late grade 3+ GI toxicities.¹⁸ Chen, et al reported a retrospective study of 52 patients receiving 36 Gy in six fractions given in two separate implants, 1 week apart. 5-year biochemical control was 51%, with a 2% incidence of grade 3 or higher late GU toxicity and no late grade 3+ GI toxicity.¹⁹

1.4 *Rationale for Salvage Regional Therapy to the Pelvic Lymph Nodes in Prostate Cancer*

There are emerging data that some patients who have recurrent disease in the pelvis may benefit from aggressive regional cancer-directed treatment with surgery or radiotherapy. Prospective studies have examined post-prostatectomy patients presenting with biochemical recurrence who underwent salvage pelvic lymph node dissection (PLND) of their [11C] choline PET/CT positive nodal disease. In a study by Rigatti et al 83.3% of patients with positive nodal metastases on [11C] choline PET/CT, had pathologic positive prostate cancer.²⁰ Following salvage lymph node dissection, a total of 41 patients (56.9%) had a subsequent biochemical response (defined as PSA <0.2). Ultimately, they found a 5-yr biochemical-free survival rate of 19% and concluded that salvage lymph node dissection in patients with nodal uptake on [11C] choline PET/CT can lead to a delay of clinical progression and a complete biochemical response can be achieved in a small proportion.

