9.0 MEASUREMENT OF EFFECT

9.1 *Antitumor Effect- Solid Tumors*

9.1.1 Definitions:

Evaluable for toxicity: All patients will be evaluable for toxicity immediately following brachytherapy.

Evaluable for disease control assessment: All patients with at least 2 follow-up PSAs will be evaluable for disease control. After brachytherapy, these patients will have their disease status classified according to the definitions stated below.

Biochemical (PSA) recurrence (BR): Based on RTOG Phoenix definition: an increase of the PSA level at least 2 ng/ml greater than the minimum level after therapy (REF: phoenix paper)

All patients with BR should undergo at least MP-MRI of the prostate and bone scan. Biopsy of any suspicious lesions within the prostate gland on MP-MRI is encouraged.

Freedom from Biochemical (PSA) Recurrence (FFBR):

The time to PSA failure will be measured from the date of treatment to the date of a rise by 2 ng/mL or more above the nadir PSA. The time of failure will be the date of the first PSA that is 2 ng/mL or more above the lowest prior post-treatment PSA value. If the rise in PSA to $>$ nadir + 2 occurs during the first 36 months followed by a subsequent non-hormonal induced PSA decrease, patients will **not** be considered PSA failures.

As a benign “spike” or “bounce” in the PSA value has been described in as many as 35% of patients 12-36 months following brachytherapy, intervention for a PSA failure should be based on a positive prostate biopsy at least 24 months post-treatment and/or clinical evidence of distant relapse (i.e., bone scan, CT scan, etc).

Local Failure (LF): This rating will be assigned when there is biopsy-proven disease progression or recurrence at the lesion within the prostate treated with protocol therapy. Histologic criterion for local failure is the presence of prostatic carcinoma upon biopsy more than 2 years after the start of treatment. Residual carcinoma on biopsy should show minimal radiation effect and should be in clinical scenario of increasing PSA.

Local Control (LC): Absence of local failure. This will be assumed in patients with a controlled PSA and for those with PSA failure but no radiographic, clinical, or biopsy-proven disease at the lesion treated with protocol therapy.

Freedom from Local Failure (FFLF): The time to local progression will be measured from the date of treatment to the date of local failure.

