Elsewhere Prostate Failure (EPF): This rating will be assigned when there is biopsy-proven disease progression/recurrence at outside the lesion treated with protocol therapy but within the prostate or seminal vesicles.

Elsewhere Prostate Control (EPC): Absence of EPF. Will be assumed in patients with a controlled PSA and in patients with PSA failure but no radiographic, clinical, or biopsy-proven disease at the site treated with protocol therapy.

Freedom from Elsewhere Prostate Failure (FFEPF): The time to elsewhere prostate failure will be measured from the date of treatment to the date of EPF.

Regional Failure (RF): Visible disease on imaging that occurs in lymph nodes within the usual regional spread pattern of prostate cancer

Regional Control (RC): Absence of regional/nodal recurrence.

Freedom from Regional Failure (FFRF): The time to regional failure will be measured from the date of treatment to the date of RF.

Distant Metastasis (DM): Visible disease on imaging that occurs elsewhere in the body including non-regional lymph nodes.

Freedom from Distant Metastasis (FFDM): The time to distant metastasis will be measured as the date of treatment to the date of DM.

Freedom from hormone therapy (FFHT): The time from the date of treatment to first administration of androgen deprivation therapy

Disease-free Survival (DFS): Defined as the duration of time from the date of completion of treatment to either BR, LF, EPF, RF, DM, or death.

Cause-specific Survival (CSS): Defined as the duration of time from the date of completion of treatment to death from prostate cancer.

Overall Survival (OS): Defined as the duration of time from the date of completion of treatment until death from any cause.

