12.0 STATISTICAL CONSIDERATIONS

12.1 *Study Design/Study Endpoints*

The primary outcome will be any radiotherapy-related acute or chronic grade 3-5 toxicity as defined previously in the document. The study is designed as a two stage Phase II study as described below.

12.2 *Sample Size and Accrual*

Primary Aim

In this single-arm oncology trial evaluating the safety and efficacy of HDR brachytherapy for recurrent prostate cancer, one goal is to determine the toxicity

of single fraction focal treatment. Simon's two-stage²³ design is used to power this aim. The primary hypothesis is that the acceptable toxic response rate is less than or equal to 10.0% (p_1). The unacceptable toxic rate is set at 33% (p_0).

More concisely:

$$H_0: p_0 \geq .33$$

$$H_A: p_1 \leq .10$$

The null hypothesis is that the unacceptable toxic response rate is at least 33%. This will be tested against a one-sided alternative that the toxicity rate is 10% or less.

In the first stage, 7 patients will be accrued. If there are 2 or more toxic responses (radiation-related acute grade ≥ 3 GU or GI toxicity) in these 7 patients, the study will be stopped for safety reasons. Otherwise, 17 additional patients will be accrued for a total of 24 patients. Note that, under these conditions, the probability of stopping early is 73% if the toxic response rate is truly higher than 10.0%.

At the end of the second stage, the null hypothesis that the toxicity rate is 33% or higher will be rejected if more than 19 (non-toxic) responses are observed in 24 patients. When the true toxicity rate is 10.0%, this design yields a type I error rate of .046 and power of 81%.

Secondary Aim

We also will describe the freedom from biochemical recurrence, relapse-free survival, local control, elsewhere-prostate control, freedom-from local failure, freedom from distant metastasis, freedom from hormonal therapy, disease-free survival, cause-specific survival, and overall survival.

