12.3 Data Analyses Plans

For this single group trial, summary frequencies and statistics will be provided for all relevant patient characteristics and clinical measures, including demographics (e.g., age, cancer stage, educational attainment, etc) as well as clinical outcomes (e.g., laboratory monitoring, adverse event monitoring, etc.). These include valid counts with percentages for categorical and ordinal variables as well as median with interquartile range or mean with standard deviation or standard error for continuous variables.

For the primary aim, a one-tailed one-sample test for proportions will be used to test whether the observed toxicity rate is lower than the hypothesized toxicity rate. For relapse-free survival, death will *not* be considered a competing event.

Instead, a two-sided one-sample log-rank test will be used to estimate the probability of being relapse free 24 months following treatment.

The instantaneous risk of relapse or death may be estimated as a function of age, cancer stage, and other covariates using semi-nonparametric Cox proportional hazards models. For these models, the number of covariates used for the adjustment will be determined by the number of events. Approximately one predictor for every 10 relapse or mortality events may be used to determine adjusted survival probabilities as described by Peduzzi et al.²⁴ For all Cox proportional hazards models, the proportional hazards assumption will be evaluated using Martingale residuals as described by Lin, Wei, and Ying.²⁵ If the proportional hazards assumption is violated, parametric accelerated failure time models may be used assuming the true underlying hazard distribution is identified.

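### Section 12.3 relies on a one-sample log-rank test to estimate 24-month relapse-free survival; the test yields no probability and has no reference curve

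*Combined protocol and SAP*

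**What the plan says.** Section 12.3 (Data Analyses Plans) is the only place that commits to a method for RFS: "a two-sided one-sample log-rank test will be used to estimate the probability of being relapse free 24 months following treatment". The sentence before it says that death will not be treated as a competing event for this outcome. It does not say whether death is an event or is censored.

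The rest of the plan adds little:

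- **Section 12.2, Secondary Aim** (repeated in the Study Summary): "We also will describe the freedom from biochemical recurrence, relapse-free survival, local control, elsewhere-prostate control", followed by further outcomes. No method is named.
- **Section 12.3, regression models:** "The instantaneous risk of relapse or death may be estimated as a function of age, cancer stage" and other covariates. These Cox models, and the accelerated failure time fallback, are optional.
- **Section 12.3, summaries:** counts with percentages, and means or medians with a measure of spread.
- **Sections 2.3.2 and 9.1.1:** neither lists nor defines RFS. The nearest defined outcome is disease-free survival: "Defined as the duration of time from the date of completion of treatment to either BR, LF, EPF, RF, DM, or death".
- **Time origin in section 9.1.1:** the freedom-from-failure outcomes run from the date of treatment. Disease-free, cause-specific and overall survival run from its completion. The Study Summary describes treatment as "2 brachytherapy implants, ~5-8 weeks of daily radiation, 6 months hormonal therapy".

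**The concern.** The sentence asks a hypothesis test to do an estimator's job. Followed literally, it cannot produce the 24-month figure it promises. The test also needs a reference survival curve to give even a p-value, and the plan supplies none. Whoever runs the analysis would have to choose a reference after the data exist, and that choice would drive the result.

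Nothing else in the plan fills the gap. Patients may withdraw or be lost to follow-up (section 8.4), so censoring has to be expected, and counts with percentages do not handle it. The same gap affects the other time-to-event outcomes listed in section 12.2.

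The stake is moderate. RFS carries no decision rule, but it is the only efficacy outcome with both a time point and a committed method. Section 1.5 says the data are meant to inform a phase III study.

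**Working it through.** **1. The plan's own design figures.** The only design calculation in the documents is the two-stage toxicity rule: continue if at most 1 of 7 patients has a toxic response, and reject the null if at most 4 of 24 do. Exact binomial calculation gives a type I error of 0.0462 at 33% (stated .046), power of 0.809 at 10% (stated 81%) and early stopping of 0.730 at 33% (stated 73%). These reproduce, but they concern toxicity and supply no input for a relapse test.

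**2. What the named test computes.** Z = (O − E)/√E, where O is the observed number of events and E is the sum, over patients, of the reference cumulative hazard up to the end of each patient's follow-up. Without a reference curve there is no E. The output is Z and a p-value.

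**3. What an estimator gives without a reference.** All relapse data from here on are assumed: 24 patients (the plan's maximum) and 7 events by 24 months.

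- *No censoring before 24 months.* S = 17/24 = 0.708; SE = √(0.708 × 0.292/24) = 0.0928; log-log 95% CI 48.4% to 84.9%.
- *Four patients lost early.* Events of 1, 2, 2 and 2 at months 6, 12, 18 and 24; two patients censored after month 12 and two after month 18; numbers at risk 24, 23, 19 and 15. S = (23/24)(21/23)(17/19)(13/15) = 0.679; Greenwood SE 0.1016; log-log 95% CI 43.8% to 83.4%.
- *Raw percentages for those same patients.* 13/24 = 54.2% if the four count as failures, 13/20 = 65.0% if excluded, 17/24 = 70.8% if counted as relapse-free.

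**4. How the test depends on the reference.** Assume exponential event times matching 17/24 at 2 years. The hazard is −ln(0.7083)/2 = 0.1724 per year, and person-years are 24 × (1 − 0.7083)/0.1724 = 40.60. As trial references, take three 5-year biochemical rates from the Background: 19% (salvage node dissection), 51% (a retrospective salvage HDR series) and the "5-year biochemical recurrence free survival of 68.9"% of the phase II salvage HDR study. Converting each to a constant hazard gives E = (−ln S5/5) × 40.60.

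| 5-year reference | E | O/E | Z | log-rank p | exact Poisson p (doubled tail) |
|---|---|---|---|---|---|
| 19% | 13.48 | 0.52 | −1.77 | 0.077 | 0.084 |
| 51% | 5.47 | 1.28 | 0.66 | 0.51 | 0.62 |
| 68.9% | 3.02 | 2.31 | 2.29 | 0.022 | 0.070 |

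The same 7 events move from fewer than expected to more than expected. The 24-month estimate from the data stays at 70.8%.

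**The case against.** The strongest reply is that this is loose wording for one descriptive outcome in a 24-patient toxicity trial, and that any statistician would use Kaplan-Meier anyway. The point about weight stands: nothing depends on this test and the primary analysis is untouched. The rest concedes that the written plan would have to be departed from.

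A second reply is that the test can be turned into a probability, as S0(24) raised to the power O/E. That is true, but only with a reference curve and a proportional-hazards assumption, and the plan states neither.

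A third is that the table in the working is invented. That also stands. Event counts, times and censoring are assumed. The borrowed rates are 5-year biochemical outcomes in other populations, and the 19% comes from surgery after prostatectomy. The constant hazards are a further assumption. The table shows dependence on the reference and nothing more.

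Some stronger inferences are tempting, and the documents do not support them:

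- *That one of the background rates is the intended reference, or that a significant result would follow.* No rate is designated as a comparator. The one p-value below 0.05 (0.022) is a normal approximation with 3.0 expected events; the exact value is 0.070.
- *That the plan already counts death as an RFS event.* Saying that death is not a competing event is compatible with counting it or with censoring it. The Cox sentence refers to relapse or death, but it may describe separate models.
- *That the section 9.1.1 failure rules make a 24-month figure unobtainable.* The histologic criterion for local failure is "presence of prostatic carcinoma upon biopsy more than 2 years after the start of treatment", and a PSA rise that "occurs during the first 36 months followed by a subsequent non-hormonal induced PSA decrease" is not counted as failure. Both bear on a 24-month landmark, but only if local failure and biochemical recurrence count as relapse, which the plan does not say. Biochemical recurrence may also register before a biopsy does. This is a separate and secondary matter of endpoint definition.

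**Conclusion.** The point holds. The one committed RFS analysis cannot be run as written and would not yield the quantity it names if it could. This rests on what the test is and on the absence of a reference curve, null 24-month rate, alpha or Kaplan-Meier method from the documents, not on the illustrative numbers.

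No real size can be calculated, because no relapse data or reference exist. On the assumed data, the choice among three background rates moves expected events from 13.5 to 3.0 against 7 observed. With four early losses, raw percentages span 54.2% to 70.8% against a Kaplan-Meier estimate of 67.9%.

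The plan should be corrected, but the trial's primary conclusion does not depend on it: RFS is secondary and descriptive, and the toxicity figures reproduce.

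**What to change.** Replace the log-rank sentence in section 12.3 with: *RFS will be estimated by the Kaplan-Meier method and the 24-month probability reported with a 95% confidence interval.* Name the same estimator for the other time-to-event outcomes where censoring of deaths is appropriate. Delete the one-sample log-rank test, or keep it only with a justified reference curve and an alpha, both fixed before analysis.

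In the same edit the investigators should:

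- state which events count for RFS, including whether death is an event or is censored;
- state one time origin, because section 9.1.1 uses both the date of treatment and the date of its completion, and treatment has several components.

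Separately, if local failure and biochemical recurrence count as relapse, the investigators should reconcile the 24-month landmark with the biopsy and PSA rules in section 9.1.1.

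The core change costs one replacement sentence, one line extending the estimator to the other outcomes, and one endpoint definition. It needs standard software and no extra data. Reconciling the section 9.1.1 rules would be additional drafting.

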13.0 STUDY MANAGEMENT

13.1 *Conflict of Interest*

13.1.1 Any investigator who has a conflict of interest (patent ownership, royalties, or financial gain greater than the minimum allowable by their institution, etc.) must properly disclose this conflict of interest per the University conflict of interest policy. All investigators will follow the institutional conflict of interest policy.

13.2 *IRB Approval and Consent*

13.2.1 It is expected that the IRB will have the proper representation and function in accordance with federally mandated regulations. The IRB should approve the consent form and protocol.

13.2.2 In obtaining and documenting informed consent, the investigator should comply with the applicable regulatory requirements, and should adhere to Good Clinical Practice (GCP) guidelines and to ethical principles that are outlined in the Declaration of Helsinki.

13.2.3 Prior to recruitment and enrollment onto this study, the patient will be provided with a full explanation of the study and will be given the opportunity to review the consent form. Each consent form must include all the relevant elements currently required by the Food and Drug Administration (FDA) regulations and local or state regulations. Once this essential information has been provided to the patient and the investigator is assured that the patient understands the implications of participation in the study, the patient will be asked to give consent to participate in the study by signing an IRB-approved consent form.

13.2.4 Prior to a patient's participation in the study, the written informed consent form should be signed and personally dated by the patient and by the individual who conducted the informed consent discussion.

13.3 *Informed Consent*

The investigator is responsible for ensuring that no patient participates in any study-related examination or activity before that patient has given informed consent. The informed consent will be provided both through the written informed consent document and through verbal review of all information contained therein. Information provided in this way is to include potential benefits, aims of the study, potential harms or side effects and methods of the study. The patient will be given opportunity to ask questions about any aspect of the information and will be given time to review the information on their own. The patient may, after having been provided with this detailed written and verbal information, provide written consent. The patient will then be provided a copy of the executed informed consent for their reference. The patient is free to withdraw consent at any time and for any reason. The only consequence of consent withdrawal is that the patient is no longer able to participate in the study.

13.4 *Protected Health Information*

In accordance with the Health Information Portability and Accountability Act (HIPAA), patients who have provided written informed consent must also sign a subject authorization to release medical information to the study sponsor and allow a regulatory authority, or the IRB access to the subject's medical information relevant to the study. This authorization may be combined with the informed consent form in accordance with the institutional practice.

13.5 *Data Management and Monitoring/Auditing*

Study-specific instructions regarding the entry and submission of data using CRFs is available through the Radiation Oncology Research Office. The Internal and Affiliate Data Compliance Policies of the Cardinal Bernardin Cancer Center's DMC will be strictly enforced.

